## LIST OF ABBREVIATIONS

ACIP	Advisory Committee on Immunization Practices (CDC)
AE	adverse event
AGM	African green monkey
AIDS	acquired immunodeficiency syndrome
BSC	biologic safety cabinet
CACI	compounding aseptic containment isolator
CDC	Centers for Disease Control and Prevention
cDNA	complementary deoxyribonucleic acid
CFR	Code of Federal Regulations
CGMP	Current Good Manufacturing Practice
CI	confidence interval
CIR	Center for Immunization Research
CL	clinical lot
cp	cold-passaged
CRADA	Cooperative Research and Development Agreement
CRF	case report form
CRL	Charles River Laboratories
CSO	Clinical Safety Office
CTM	clinical trial material
DAERS	DAIDS Adverse Event Reporting System
DAIDS	Division of AIDS
DAIDS PRO	Division of AIDS Protocol Registration Office
DC	discontinuation
DCR	Division of Clinical Research
DHHS	Department of Health and Human Services
DMC	Data Management Center
DMEM	Dulbecco's Modified Eagle Medium
DNA	deoxyribonucleic acid
DSMB	Data and Safety Monitoring Board
EAE	expedited adverse event
EENT	ears, eyes, nose, throat
ELISA	enzyme-linked immunosorbent assay
F protein	fusion protein
FDA	Food and Drug Administration
FDAAA	Food and Drug Administration Amendments Act of 2007
FSTRF	Frontier Science & Technology Research Foundation, Inc.
GCP	Good Clinical Practice
GLP	Good Laboratory Practice
GMP	Good Manufacturing Practice
GMT	geometric mean titer
HIPAA	Health Insurance Portability and Accountability Act
HIV	human immunodeficiency virus
HJF	Henry M. Jackson Foundation for the Advancement of Military Medicine
IB	investigator's brochure
ICD	informed consent document
ICH	International Conference on Harmonisation
IgA, IgG, IgE	immunoglobulin A, G, E
IMPAACT	International Maternal Pediatric Adolescent AIDS Clinical Trials Network
i.n.	intranasally
IND	investigational new drug

IoR	Investigator of Record
IRB	institutional review board
i.t.	intratracheally
JHSPH	Johns Hopkins Bloomberg School of Public Health
JHU	Johns Hopkins University
LDMS	Laboratory Data Management System
LID	Laboratory of Infectious Diseases
LPC	laboratory processing chart
LRI	lower respiratory illness
LRT	lower respiratory tract
MA-LRI	medically attended lower respiratory illness
MOP	manual of procedures
mRNA	messenger ribonucleic acid
NHP	nonhuman primate
NIAID	National Institute of Allergy and Infectious Diseases
NIAID CRMS	NIAID Clinical Research Management System
NICHD	National Institute of Child Health and Development
NIH	National Institutes of Health
nt	nucleotide
OCRPRO	Office of Clinical Research Policy & Regulatory Operations
OHRP	Office for Human Research Protections
ORF	open reading frame
OTC	over-the-counter
PBMC	peripheral blood mononuclear cell
PCR	polymerase chain reaction
PE	physical examination
PFU	plaque-forming units
PI	principal investigator
PID	participant identification number
PRNT	plaque reduction neutralization
PSRT	Protocol Safety Review Team
r	recombinant
RE	regulatory entity
RNA	ribonucleic acid
rRT-PCR	reverse transcription polymerase chain reaction
RSC	Regulatory Support Center
RSV	respiratory syncytial virus
RT-qPCR	quantitative reverse transcription polymerase chain reaction
SAE	serious adverse event
SAM	synthetic absorptive matrix
SDAC	Statistical & Data Analysis Center, Harvard School of Public Health
SDMC	Statistical and Data Management Center
SERF	Safety Expedited Report Form
SES	subject enrollment system
SID	study identification number
SMM	sponsor medical monitor
SOP	standard operating procedure
SPG	sucrose-phosphate-glutamate buffer
SRCP	Safety Review and Communication Plan
SUSAR	serious, unexpected, suspected adverse reaction
TL	tracheal lavage
ts	temperature sensitivity
T SH	shut-off temperature
T SP	small plaque temperature

UP	unanticipated problem
URI	upper respiratory tract illness
URT	upper respiratory tract
US	United States
VAR	vaccine administration record
WIRB	Western Institutional Review Board
wt	wild-type
$\Delta$ M2-2	deleted M2-2

## PROTOCOL SUMMARY

### **Phase I Placebo-Controlled Study of the Infectivity, Safety and Immunogenicity of a Single Dose of a Recombinant Live-attenuated Respiratory Syncytial Virus Vaccine, RSV 6120/ΔNS2/1030s, Lot RSV#012A, Delivered as Nose Drops to RSV-Seropositive Children 12 to 59 Months of Age and RSV-Seronegative Infants and Children 6 to 24 Months of Age**

SHORT TITLE	RSV 6120/ΔNS2/1030s
PURPOSE	To determine whether study vaccine is attenuated and immunogenic in this age group
DESIGN	A double blind, randomized, placebo-controlled study design will be used to evaluate the safety and immunogenicity of the study product in RSV-seropositive and RSV-seronegative participants.
STUDY POPULATION	Group 1: Healthy RSV-seropositive* children $\geq$ 12 months to < 60 months of age Group 2: Healthy RSV-seronegative ^ infants and children $\geq$ 6 months to < 25 months of age
	*RSV-seropositive: RSV serum neutralizing antibody titer $\geq$ 1:40; determined prior to inoculation and within the calendar year of inoculation
	^ RSV-seronegative: RSV serum neutralizing antibody titer < 1:40; determined $\leq$ 42 days prior to inoculation
SAMPLE SIZE	Group 1: Approximately 15 RSV-seropositive children Group 2: Approximately 21-30 RSV-seronegative infants and children
STUDY PRODUCT	Single dose of intranasal RSV 6120/ΔNS2/1030s vaccine or placebo

**Table 1: Inoculation Schedule**

Group #	N	Study Product	Dose
1	10	RSV 6120/ΔNS2/1030s	$10^{5.7}$ PFU*
	5	Placebo	0
2	14-20	RSV 6120/ΔNS2/1030s	$10^{5.0}$ PFU*
	7-10	Placebo	0

\*plaque-forming units (PFU)

[figure not shown]
The study will start with group 1 and proceed to group 2 if there are not more than 2 vaccine-associated solicited adverse events (AEs) (Days 0 through 10) and no vaccine-associated lower respiratory illnesses (LRIs) (Days 0 through 28) in RSV-seropositive children. If 3 or more RSV-seropositive children (group 1) have respiratory or febrile illness that coincides with shedding of  $> 10^{2.5}$  PFU of vaccine virus as detected by culture, then we will evaluate the safety, infectivity, and immunogenicity of the vaccine virus in an additional 15 RSV-seropositive children before determining whether to continue with group 2.

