## **3 STUDY DESIGN**

The study will be double-blind, randomized, and placebo-controlled. Participants in groups 1 and 2 will be block-randomized in groups of 3 at a ratio of 2:1 to receive vaccine or placebo, respectively. The vaccine will be evaluated in a stepwise fashion beginning with RSV-seropositive children (Group 1) and proceeding sequentially in RSV-seronegative children (Group 2). For the purpose of this study, RSV-seropositive is defined as having a serum neutralizing antibody titer of  $\geq 1:40$ , and RSV-seronegative is defined as having a serum neutralizing antibody titer of  $< 1:40$ . This definition has been used in previous evaluations of live-attenuated RSV vaccines (11, 24, 35). In these previous studies, live-attenuated RSV vaccines were highly restricted in replication and poorly immunogenic in children with titers  $\geq 1:40$  but were far less restricted in replication and highly immunogenic in children with titers  $< 1:40$ . These data suggest that this neutralizing antibody cutoff can distinguish effectively between RSV-experienced and RSV-naïve children.

The study will proceed to group 2 if there are not more than 2 vaccine-associated solicited AEs and no vaccine-associated LRIs in RSV-seropositive children. If 3 or more RSV-seropositive children have respiratory or febrile illness that coincides with shedding of  $> 10^{2.5}$  PFU of vaccine virus as detected by culture, then we will enroll an additional 15 RSV-seropositive children to continue evaluating the safety, infectivity, and immunogenicity of the vaccine virus.

Enrollment occurs at the time of inoculation with study product, Day 0, and will occur between April 1 and October 31 to avoid the time during which wt RSV typically circulates in the community ([Appendix V](#), Figure 6). Accrual will stop prior to November 1.

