## 4 STUDY POPULATION

Approximately 15 RSV-seropositive children  $\geq$  12 months to  $<$  60 months of age will be enrolled; 10 will receive a single dose of  $10^{5.7}$  PFU of vaccine and 5 will receive a single dose of placebo. Subsequently, 21 to 30 RSV-seronegative infants and children  $\geq$  6 months to  $<$  25 months of age will be enrolled in the study and will receive a single dose of either  $10^{5.0}$  PFU of vaccine or placebo in a 2:1 ratio. These numbers were chosen based upon experience with phase I evaluation of other live-attenuated respiratory virus candidate vaccines ([11,23,25](#)) and statistical considerations (Section 9).

Placebo recipients are needed in pediatric studies to distinguish the background respiratory and febrile illnesses that occur in infants and children from those attributable to study vaccine. These numbers were chosen based upon experience with phase I evaluation of other live-attenuated respiratory virus candidate vaccines ([11,23,25](#)) and statistical considerations (Section 9).

Infants and children will be selected for participation according to the described study-specific co-enrollment considerations; the recruitment, screening, and enrollment process; and participant retention and withdrawal or termination.

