## 6.5 STUDY PHASES

Refer to [Figures 1](#) and [2](#) for timelines of study visits. The Acute Phase begins with inoculation and ends at midnight on the 10th day after inoculation for RSV-seropositive participants, and at midnight on the 28th day after inoculation for RSV-seronegative participants. During the Acute Phase of the study, a study healthcare professional will be available by telephone 24 hours a day for consultation with parent/guardian regarding any illnesses that may occur.

Study personnel will have daily contact with RSV-seropositive participants' parents/guardians for the first 10 days after inoculation, and for the RSV-seronegative participants during the first 28 days after inoculation. This 28-day period is consistent with the duration of shedding of live-attenuated respiratory virus vaccines in RSV-seronegative participants ([28](#), [37-39](#)).

On non-visit days, study staff will contact the parent/guardian and will record the parent/guardian-provided temperatures and signs of illness. Participants with illness may have additional visits to assess the illness (Section [6.8](#), Illness Visit).

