#### 6.5.1.4 Post-Acute Phase

The Post-Acute Phase begins on the 11th day after inoculation and ends on the 28th day after inoculation. During the Post-Acute Phase, parent/guardian will be instructed to monitor for and contact the study staff if their child has symptoms that are suggestive of a SAE. If the parent reports an SAE that may meet the study pause or stop criteria (Section 8.3), then an Illness Visit will be scheduled (Section 6.8).

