**Table 8: Day 28 Visit Procedures – RSV-Seropositive Children**

Day 28 Visit (+7 Days)	
Administrative Tasks	

Provide study compensation

Clinical Tasks	

Obtain and document from parent/guardian the participant's interim history from midnight of the 10th day through the 28th day following inoculation, including:

visits to medical provider/hospitalizations

medications and/or immunizations

signs and symptoms of illness meeting SAE criteria

Address any concerns

Review safety data

Document findings

Laboratory Tasks	Collect blood for: 

Serum antibodies to RSV

	Collect nasosorption strip for: 

RSV antibody assays

 
Note: The nasosorption must be performed prior to the nasal wash.
 
The nasal wash must be obtained prior to administering the study product.
 Collect nasal wash for: 

RSV antibody assays

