**Table 16: Illness Visit Timeframe**

Illness Visit Timeframe			
Phase	Symptoms	Grade	Visit Timeframe
Acute	Fever, otitis media or URI	1	Within 3 days
Acute	Fever, otitis media or URI	$\geq 2$	Within 2 days
Acute	LRI	Any	Within 1 day
Post-Acute	SAE that meets study pause or stop criteria (Section 8.3)	$\geq 2$	Within 3 days
RSV Season Surveillance	Medically attended fever, otitis media, URI or LRI	$\geq 2$	Within 3 days

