**Table 19: AE CRF Recording Requirements for RSV-Seropositive Subjects**

Study Phase at the Time of Event Onset	Calendar Date	AEs to Record on CRFs	Concomitant Medications to Record on CRFs
Day 0 through midnight of 10 th day following inoculation (Acute Phase)	ANY	
 
• All SAEs
 
• All solicited AEs that meet Appendix IV, criteria
 
• All unsolicited AEs (Grades 1 to 4), with the exception of the following conditions if not treated with prescription medication or non-prescription medications with antipyretic properties: diaper rashes, teething pain, and spitting up
 
	
Record these medications on the CRFs regardless of whether the related event is recorded on the CRFs:
 
 
• All cough and cold remedies including decongestants, cough suppressants, expectorants
 
• All nasal sprays (except saline spray)
 
• All antihistamines
 
• All antipyretics
 
• All prescription medications
 
 
For SAEs and LRIs:
 
 
• All medications related to the recorded event
 

From the 11 th day after inoculation to the 28 th day after inoculation (Post-Acute Phase)	ANY	
 
• All LRIs and SAEs
 
	
 
• All medications related to the recorded event
 

Throughout study	ANY	
 
• Unresolved AEs or SAEs with onset from Day 0 to midnight on the 10th day after inoculation
 
• Unresolved LRIs and SAEs with onset prior to the 28th day following inoculation
 
• 
 
	
 
• All medications related to the recorded event
 

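### The rule for opening Group 2 counts Group 1 lower respiratory illness through Day 28, but on Days 11–28 non-serious cases are captured only passively, late and incompletely

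*Combined protocol and SAP*

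**What the plan says.** **What has to be known.** The Protocol Summary (text under Table 1) makes progression to Group 2 depend on there being "no vaccine-associated lower respiratory illnesses (LRIs) (Days 0 through 28) in RSV-seropositive children". It gives other solicited adverse events a separate window of Days 0–10. Section 3 repeats the rule without any window: "if there are not more than 2 vaccine-associated solicited AEs and no vaccine-associated LRIs in RSV-seropositive children". For Group 1 onsets on Days 11–28, Table 19 requires the case report form to hold "All LRIs and SAEs". The matching Group 2 row in Table 20 lists SAEs alone.

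**How it would be found.**
- Section 6.5: "Study personnel will have daily contact with RSV-seropositive participants' parents/guardians for the first 10 days after inoculation". A Day 11 contact then closes the history at midnight on Day 10 (Section 6.5.1.3).
- Section 6.5.1.4: from Day 11 parents are "instructed to monitor for and contact the study staff if their child has symptoms that are suggestive of a SAE". Section 3 describes the same arrangement.
- Table 16: the single Post-Acute trigger for an Illness Visit is an "SAE that meets study pause or stop criteria (Section 8.3". The footnote to Table 30 restricts the interim Post-Acute tasks in the same way.
- Table 8: the symptom item at the Day 28 visit is "signs and symptoms of illness meeting SAE criteria". The table also asks about provider visits and medications. It lists no examination, and its nasal wash is for antibody assays only. Section 6.5.1.5 allows this visit up to Day 35.

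**Other windows.** Section 6.10.2 provides for illness washes through Day 28 in Group 1. Expedited LRI reporting (Section 7.3) and the LRI pausing rule (Section 8.3, Table 23) stop at Day 10 for Group 1.

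**The concern.** The progression rule and the recording table look to Day 28, while the procedures that would bring a non-serious LRI to the staff's attention largely end at Day 10. The addition of LRIs to the Group 1 row, absent from the Group 2 row, suggests that the longer window was deliberate but was not carried into the Post-Acute procedures.

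An LRI is also hard to reconstruct afterwards. Appendix IV asks, for each type, that the finding be sustained over 20 minutes and assessed by a medical professional. Whether it was associated with the vaccine is easier to judge with a nasal wash taken during the illness.

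The virus is being given to humans for the first time (Section 1.2.3). Ten vaccinated seropositive children inform its use in seronegative children from 6 months of age, and Section 9.3.1 treats an LRI in a child infected with vaccine virus as the key warning event. A count of zero is informative only to the extent that cases were looked for.

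**Working it through.** **Plan figure.** The documents give no error rate or detection probability for the Group 1 rule, so there is none to reproduce. The nearest figures are in Table 24 (Group 2, N = 20), which rests on the same binomial reasoning. At a true rate of 10%, the probabilities of 0, 1 or more, and 2 or more events compute to 0.122 (= 0.9^20), 0.878 and 0.608, against 0.12, 0.88 and 0.61 stated. All 15 cells reproduce.

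**Days.** Days 0–28 are 29 study days and Days 0–10 are 11 of them. The remaining 29 − 11 = 18 days are 18/29 = 62% of the window. No contact is scheduled between the Day 11 call and the Day 28 visit.

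**Tracing a non-serious LRI with onset on Days 11–28.**
1. The child sees no provider. The parent has not been asked to call, the Day 28 symptom item does not cover the illness, and Table 8 has no examination. No defined route leads to the Table 19 entry.
2. The child sees a provider. The provider-visit and medication items in Table 8 can bring the illness out, but only at Day 28–35. Records can be requested under the release in Section 6.1, though the 20-minute criterion may not be documented. Unless the parent happened to call, there is no wash from the time of illness.

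**Effect on the rule, as an illustration.** Let p be the true risk over Days 0–28 of an LRI that should count, q the share of such LRIs that are non-serious with onset on Days 11–28, and d the chance that one of those is captured. All three are assumptions. With 10 vaccinees (Section 4):

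P(no LRI detected) = (1 − p × (1 − q × (1 − d)))^10

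For p = 0.20 and q = d = 0.5, this is (1 − 0.20 × 0.75)^10 = 0.85^10 = 0.197, against 0.80^10 = 0.107 with full capture.

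| p | Full capture (d = 1) | q = 0.25, d = 0.5 | q = 0.5, d = 0.5 | q = 0.5, d = 0 |
|---|---|---|---|---|
| 3% | 0.74 | 0.77 | 0.80 | 0.86 |
| 5% | 0.60 | 0.64 | 0.68 | 0.78 |
| 10% | 0.35 | 0.40 | 0.46 | 0.60 |
| 20% | 0.11 | 0.15 | 0.20 | 0.35 |

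The 3% row replaces p by 0.03 in the same formula: 0.97^10, 0.97375^10, 0.9775^10 and 0.985^10.

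**The case against.** The strongest reply is that the protocol has other routes to these events.
- Table 8 asks about any provider visit and medication, not only serious ones.
- Table 19 requires all LRIs to be recorded.
- Section 6.8 allows Illness Visits in any phase, and Section 6.10.2 provides for washes through Day 28.
- Parents receive an explanation of illness criteria at enrollment (Table 4), with no end date stated.
- Relatedness is a clinician's judgement on the available information (Section 8.1), and the third stopping criterion in Section 8.3 needs no shedding result.

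All of this stands. It rules out the stronger inference that non-serious LRIs after Day 10 go wholly undetected, or that their association with vaccine cannot be judged at all. It does not close the gap: Table 19 says what to record but not how staff learn of it, and washes are of little use if nothing prompts the call.

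A second reply is that the true risk is probably small. Section 9.3.1 says LRI is rare in such studies. Section 3 reports strong restriction of earlier vaccines in seropositive children, and Section 1.2.1 reports no shedding in seropositive children for the preceding candidate. This also stands, and it limits the absolute effect: at p = 3% the central case moves the probability from 0.74 to 0.80. However, the present candidate was designed to be slightly less restricted than that predecessor.

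A third reply is that there are other safeguards: the solicited-event limit, the shedding rule and DSMB review, and in Group 2 daily contact with an LRI pause through Day 28. These reduce the consequence of a missed case, but they do not make the Group 1 observation complete.

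**Conclusion.** The inconsistency is in the text. The progression rule and Table 19 need all Group 1 LRIs through Day 28, while the parent instruction, the Post-Acute visit trigger and the Day 28 symptom item cover only SAEs for 62% of that window. Following the plan as written could satisfy the rule with non-serious LRIs missed, or learned of too late for a wash during the illness. That weakens both the Appendix IV case definition and the judgement of vaccine association.

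The size is illustrative. If half of LRIs are late and non-serious and half of those are captured, the chance of a clean result rises from 0.11 to 0.20 at 20% risk and from 0.35 to 0.46 at 10%. With none of those captured it is 0.35 and 0.60. No document figure supports any particular p, q or d.

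A reader might go further, spread the risk evenly over the 29 days and assume no capture after Day 10. That gives (1 − 0.20 × 11/29)^10 = 0.45 and (1 − 0.10 × 11/29)^10 = 0.68. The documents do not support this: it discards serious LRIs, which are solicited, and medically attended ones, which Table 8 can reach. Nor do they settle that Day 28 is the intended window throughout, given the Day 10 limits in Sections 7.3 and 8.3 and the absence of a window in Section 3.

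**What to change.** Reconcile the Protocol Summary, Section 3, Section 6.5.1.4, Table 8, Table 16, Section 6.10.2, Table 19, Section 7.3, Section 8.3 (Table 23) and Table 30, so that LRI ascertainment in Group 1 covers the same period as the progression rule. Choosing that period is for the sponsor.

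- If the Day 28 window already in the Protocol Summary and Table 19 is confirmed, carry LRI symptoms into three places: the Post-Acute parent instruction, the Post-Acute row of Table 16 for Group 1 (with the wash that Section 6.10.2 already provides for) and the Table 8 interim history. State explicitly whether the Day 10 limits on expedited reporting and pausing are meant to differ.
- If another window is intended, state it consistently, and do not describe the rule as having shown no LRI through Day 28.

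The cost is a wording amendment and, under the first option, a few unscheduled visits among about 15 children, using procedures already in the protocol. It should be settled before Group 1 results are used to open Group 2.

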## STUDY DURATION

[figure not shown]
Participants will be enrolled in the protocol between April 1 and October 31, outside of the RSV season. RSV-seropositive participants will be followed for 28 days after inoculation, and RSV-seronegative participants will remain on the study until they complete the post-RSV season visit.

After the first season of RSV surveillance is completed, research staff may invite the families of participants in group 2 to participate in an optional second season of RSV surveillance during November–March of the second year following enrollment.

**Figure 1: Group 1 – Study Overview**

**Figure 2: Group 2 – Study Overview**

\*Post-RSV Season specimens to be collected beginning April 1st

# 1 BACKGROUND AND SCIENTIFIC RATIONALE

## 1.1 BACKGROUND

### 1.1.1 Epidemiology, Disease Burden, and the Need for a Vaccine

In the United States alone, RSV is responsible for 75,000 to 125,000 hospitalizations of infants yearly (1), and worldwide, RSV infects at least 34 million children under 5 years old, resulting in an estimated 3.4 million RSV LRI hospitalizations and 66,000 to 199,000 RSV-attributable deaths each year (2). In temperate climates, annual RSV epidemics occur in late winter and early spring, and nearly all children are infected within the first 2 years of life. RSV illness can range from mild upper respiratory tract illness (URI), including rhinitis, pharyngitis, and coryza, to severe LRI, including bronchiolitis and pneumonia. Beyond the acute burden of disease caused by RSV, severe RSV disease in infancy may predispose to reactive airway disease during childhood (3, 4).

RSV is an enveloped RNA virus that is a member of the newly organized *Pneumoviridae* family, genus *Orthopneumovirus* (5). RSV has a single negative-sense strand RNA genome of 15.2 kilobases encoding 10 mRNAs. Each mRNA encodes a single protein, with the exception of the M2 mRNA, which contains 2 overlapping ORFs. The 11 RSV proteins are the viral RNA-binding nucleoprotein N, the phosphoprotein P, the large polymerase protein L, the attachment glycoprotein G, the fusion glycoprotein F, the small hydrophobic surface glycoprotein SH, the internal matrix protein M, the 2 nonstructural proteins NS1 and NS2, and the M2-1 and M2-2 proteins encoded by the M2 mRNA. The gene order is: 3'-NS1-NS2-N-P-M-SH-G-F-M2-L-5'. RSV transcription and genome replication take place exclusively in the cytoplasm, and virions form by budding from the apical plasma membrane of respiratory epithelial cells.

Currently, no licensed vaccine against RSV is available, although there is broad consensus that such a vaccine is urgently needed and should be a global health priority. Although passive immunoprophylaxis with the monoclonal RSV-neutralizing antibody palivizumab (Synagis®; MedImmune) is available for high-risk infants, this approach is not feasible for general use. A formalin-inactivated vaccine against RSV was evaluated clinically in the 1960s and did not confer protection; instead, disease enhancement occurred at a high rate following natural infection of vaccinees with wild-type (wt) RSV (6). Studies in experimental animals established that disease enhancement was specific to non-replicating RSV vaccines and not seen with infectious RSV or replicating vaccine vectors (7, 8).

Following the failure of the formalin-inactivated RSV vaccine, attempts at developing RSV vaccines at NIAID have focused largely on live-attenuated approaches (9). Importantly, throughout a period of over 20 years, a number of live-attenuated investigational RSV vaccines have been evaluated in RSV-naïve infants and children, and enhanced disease following wt RSV infection of vaccinees has not been observed (10). Apart from the absence of enhanced disease, live-attenuated RSV vaccines have a number of known advantages over non-replicating RSV vaccines. They can be administered intranasally, induce protective mucosal immunity in the respiratory tract (as well as systemic immunity), infect in the presence of maternally-derived RSV serum antibody, and have been well tolerated and immunogenic when administered to infants as young as four weeks of age (11).

Human RSV has a single serotype with two antigenic subgroups, A and B. The two subgroups exhibit a 3- to 4-fold reciprocal difference in neutralization by polyclonal convalescent serum. Analysis of glycoprotein-specific responses in infants by enzyme-linked immunosorbent assay

(ELISA) with purified F and G glycoproteins showed that the fusion proteins (F proteins) were 50% related antigenically, and the G proteins were 7% related (12). Consistent with this level of antigenic relatedness, F protein expressed by a recombinant vaccinia virus was equally protective in cotton rats against challenge with either subgroup A or B, whereas the G protein was 13-fold less effective against the heterologous subgroup (13). Thus, the F protein is responsible for most of the observed cross-subgroup neutralization and protection, and a subgroup A vaccine virus is likely to induce a broad immune response against wt RSV of either subgroup. Antibodies to the F protein are one of the endpoints evaluated in this study.

The RSV vaccines to be evaluated in this study were derived using a recombinant deoxyribonucleic acid (DNA)–based technique called reverse genetics (14). The technique of reverse genetics has been used to produce a number of licensed vaccines; among them is FluMist® (MedImmune). This technique allows *de novo* recovery of infectious virus entirely from complementary DNA (cDNA) in a qualified cell substrate under defined conditions. Reverse genetics provides a means to introduce predetermined mutations into the RSV genome via the cDNA intermediate. Derivation of vaccine virus from cDNA minimizes the risk of contamination with adventitious agents and helps to keep the passage history brief and well documented. Once recovered, the vaccine virus is propagated in the same manner as a biologically derived virus. As a result of repeated passage and amplification, the drug substance (clinical trial material [CTM]) does not contain any recombinant DNA. The RSV vaccine candidate to be tested under this protocol is a derivative of strain A2, subgroup A.

The drug substance RSV 6120/ΔNS2/1030s is a recombinant live-attenuated RSV vaccine candidate that contains a deletion of the NS2 gene (ΔNS2) and a genetically stabilized version of the attenuating temperature sensitivity mutation at codon 1321 of the L gene termed “1030s” (S1313[TCA]/Y1321K[AAA]). The RSV NS2 protein functions as an interferon antagonist, and deletion of NS2 is attenuating (15-21). The 1030s mutation is also attenuating and confers a moderate temperature-sensitive phenotype to RSV (22). RSV 6120/ΔNS2/1030s has a shutoff temperature for replication of 40°C, and it produces only small plaques at 38°C or above. Compared to recombinant wt RSV, the RSV 6120/ΔNS2/1030s candidate vaccine was significantly restricted in replication in a primary human airway epithelial cell model, and moderately attenuated and immunogenic in African green monkeys (AGM).

